8.3.2. Safety Endpoints

The safety endpoints are listed in the following:

- The incidence and severity of TEAEs
- Clinically important changes in safety assessment results [including, as appropriate, vital signs, clinical laboratory tests, ECGs, Ashworth score, falls assessment, physical and neurological examinations, BDI-Fast Screen and suicidality assessment].

8.3.3. Pharmacokinetic Measurements

The plasma concentrations of CK-2127107 and possible metabolites will be measured at the sampled time points during the study.

8.4. Statistical Analysis

8.4.1. Patient Disposition

The number and percentage of patients randomized, receiving any study drug, completing the study, prematurely discontinuing treatment and prematurely discontinuing from the study will be summarized by dose group, treatment and overall. Reasons of premature discontinuation will also be summarized.

8.4.2. Demographics and Other Baseline Characteristics

Patient demographics and other baseline characteristics will be summarized by dose group, treatment and overall using descriptive statistics.

8.4.3. Prior and Concomitant Medications

Prior and concomitant medications will be classified using the World Health Organization Drug dictionary, and summarized by drug class and preferred term (PT).

8.4.4. Efficacy Analysis

Efficacy analyses will be conducted for the FAS.

8.4.4.1. Primary Efficacy Analysis

The hypothesis for the primary efficacy analysis is that there is a positive treatment difference (CK-2127107 minus placebo) in change from baseline to Week 12 in the percent predicted SVC.

The effect of CK-2127107 on the change from baseline to Week 12 in percent predicted SVC will be analyzed using a MMRM with the contrast (-5, -1, 3, 3) to reflect the assumed relationship for the placebo, 300 mg/day, 600 mg/day and 900 mg/day dose groups. The response variable in the model will be the change in the percent predicted SVC from baseline to each post-baseline visit. The model will include the terms of treatment, baseline value, pooled site, visit, randomization stratification factors of riluzole use/non-use and stratified edaravone use/non-use, as well as treatment-by-visit and baseline-by-visit interactions. An unstructured variance-covariance structure will be used to model the within-subject errors.

8.4.4.2. Secondary Efficacy Analysis

Slope from baseline in the mega-score of muscle strength will be analyzed using a MMRM. The response variable will be the change from baseline to each post-baseline visit. The model will include the terms of treatment, the baseline value, pooled site, time, randomization stratification factors of riluzole use/non-use, and stratified edaravone use/non-use as well as treatment-by-baseline and treatment-by-time interactions. A random slope effect will be assumed in the model. Change from baseline in the ALSFRS-R will be analyzed using the same method as for the primary efficacy analysis.

8.4.4.3. Exploratory Efficacy Analysis

Exploration of the dose-response relationship will come from model-based analyses that will use various assumptions of an implicit dose-response relationship. In addition, placebo will be tested against each dose group of CK-2127107 for specified endpoints and the 600 mg/day and 900 mg/day dose groups combined.

8.4.4.4. Multiplicity

The global null hypothesis for the primary and secondary efficacy endpoints will be tested in a pre-specified order using a closed testing procedure. This procedure will maintain the family-wise error rate at two-sided significance level of 0.05 for all hypotheses tested in a confirmatory sense. Details of the procedures will be provided in the Statistical Analysis Plan.

Hypotheses other than the primary and secondary efficacy endpoints will also be tested with a significance level of 0.05. However, no adjustments for multiple comparisons will be made for these tests.

8.4.5. Safety Analysis

Safety analyses will be conducted for the SAS. Safety data will be summarized by dose group, treatment and overall using descriptive statistics.

8.4.5.1. Study Drug Exposure

The amount of study drug received and duration of study drug exposure will be summarized.

8.4.5.2. Adverse Event

AEs will be coded using the Medical Dictionary for Regulatory Activities (MedDRA) and tabulated by system organ class (SOC) and PT. Individual events (PT) within each SOC will be presented in order of descending frequency.

An AE (or SAE) will be regarded as treatment emergent if it starts or worsens (e.g., increases in severity or frequency) during or after the first dose of study drug. TEAEs will be summarized by maximum severity, and by relationship to the study treatment. All AEs will be listed.

8.4.5.3. Serious Adverse Event

Treatment emergent SAEs will be summarized by maximum severity, and by relationship to the study treatment. All SAEs will be listed.

8.4.5.4. Clinical Laboratory Parameters

For each laboratory parameter, the number and percentage of subjects with alert values or values outside the normal range during the study will be tabulated. All laboratory evaluations identified as outside the normal range or as alerts by the central laboratory will be listed. The value and change from baseline in continuous laboratory parameters will be summarized at each scheduled visit where laboratory measurements are taken.

8.4.5.5. Vital Signs

For each measurement of heart rate, blood pressure, respiratory rate, and BMI, the number and percentage of subjects with clinically relevant abnormalities during the study will be tabulated. All measurements identified as clinically relevant abnormalities will be listed. The value and change from baseline in heart rate, blood pressure, respiratory rate and BMI will be summarized at each scheduled visit where vital signs are taken.

8.4.5.6. ECGs

For each ECG measurement, the number and percentage of subjects with clinically relevant abnormalities during the study will be tabulated. ECG measurements identified as clinically relevant abnormalities will be listed. The value and change from baseline in ECG measurements will be summarized at each scheduled visit where measurements are taken.

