3. STUDY OVERVIEW

3.1. Study Design

This is a Phase 2, double-blind, randomized, placebo-controlled, dose ranging study of CK-2127107 in patients with ALS.

Approximately 445 eligible ALS patients will be randomized (1:1:1:1) to receive the following doses of CK-2127107 or placebo:

- 150 mg CK-2127107 twice a day for a 300 mg total daily dose (TDD)
- 300 mg CK-2127107 twice a day for a 600 mg TDD
- 450 mg CK-2127107 twice a day for a 900 mg TDD
- Placebo twice daily

Study medication should be taken twice daily, approximately 12 hours (\pm 2 hours) apart, and should be taken within the 2 hour period following a meal.

An overview of the randomized treatment groups is provided in [Table 1](#):

[figure not shown]
Table 1: CY 5022 Randomized, Double-Blind Treatment Groups

CK-2127107			Placebo
300 mg TDD 1 tablet (150 mg) of CK-2127107 and 2 placebo tablets twice daily for 12 weeks	600 mg TDD 2 tablets (150 mg) of CK-2127107 and 1 placebo tablet twice daily for 12 weeks	900 mg TDD 3 tablets (150 mg) of CK-2127107 twice daily for 12 weeks	3 placebo tablets twice daily for 12 weeks

The screening and qualification period for the study will be no more than 14 days in duration. Once patients have completed screening and are considered eligible for the study, they will be randomized as described above and stratified by riluzole use/non-use and edaravone use/non-use.

There will be a total of seven study visits for each patient:

- Screening
- First Dosing Day (Day 1)
- Week 2
- Week 4
- Week 8
- Week 12
- Follow-Up Visit (4 weeks after last dose of study drug)

Figure 1: Patient Visit Diagram

PD measures, vital signs, electrocardiograms (ECGs), and clinical laboratory evaluations will be performed at Screening and at specified times during the study. Patients will be evaluated at each study visit for signs and symptoms of intolerance to study drug.

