5.4. Week 4 Visit

Prior to study drug dosing at the Week 4 Visit, the following procedures will be performed:

1. 12-lead ECG
2. Vital signs, including heart rate, blood pressure, and respiratory rate measured after the patient has been resting for at least 3 minutes
3. Weight and calculation of BMI
4. PK blood sample
5. Clinical laboratory evaluations, including CBC and WBC with differential, serum chemistries, cystatin C and UA

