5.13. Clinical Safety Assessments

5.13.1. Clinical Laboratory Evaluations

Clinical laboratory evaluations will be collected at Screening, Day 1, Week 2 visit, Week 4 visit, Week 12 visit, and at the Follow-Up Visit as described in [Appendix D](#).

5.13.2. 12-Lead Electrocardiograms

A 12-lead ECG, including ECG parameters of RR, PR, QRS, QT and QTc intervals as well as significant findings will be obtained at Screening, Week 4 visit, and at the Follow-Up Visit.

When 12-lead ECGs are scheduled at the same time as blood draws, the order of evaluation will be ECG, vital signs, and then blood draw.

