8.6. Electrocardiogram

A 12-lead ECG, including ECG parameters of RR, PR, QRS, and QT intervals as well as significant findings will be obtained at Screening, Week 4 and Follow-Up Visits. Descriptive statistics of absolute value and change from baseline of ECG parameters (PR interval, RR interval, QRS duration, QT interval, QTc interval [Bazett’s and Fridericia’s], Ventricular Heart Rate) will be presented at each assessment time point by dose level and overall.

The number and percentage of patients who had normal or missing values at baseline and PCS values post baseline will be presented by dose level and overall. ECG parameters are regarded as PCS if the value meets the criterion shown in Table 7. For each parameter, the denominator of the percentage will include patients with non-PCS or missing assessments at baseline, and with at least one assessment post baseline. The numerator of the percentage will include patients who had at least one PCS assessment post baseline among the patients that were counted in the denominator. Assessment collected at an unscheduled visit or the Follow-up Visit will also be included in the summary.

Twelve-lead ECG parameters (PR interval, QRS duration, QT interval, QTc interval [Bazett’s and Fridericia’s], Ventricular Heart Rate, and RR interval), will be listed with dose level, patient ID, visit and assessment date and time. PCS ECG values will be flagged. ECG findings and interpretations will be listed as well.

Table 7: Criteria of Abnormal and PCS ECG Values

ECG Variable	Units	Upper Limit of Normal	PCS High Values
QRS Interval	msec	80	≥120
PR Interval	msec	200	≥240
QTcB Interval	msec	Males: 450 Females: 460	>500
QTcF Interval	msec	Males: 450 Females: 460	>500
QT Interval	msec	—	> 500
Ventricular Heart Rate	bpm	—	>100

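### The abnormality counts for ECG, laboratory and vital signs mix on-drug with drug-free assessments, and no on-treatment count by arm is planned (minor)

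*Protocol*

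**What the plan says.** Protocol 8.4.5.6 sets the period as the whole study: "For each ECG measurement, the number and percentage of subjects with clinically relevant abnormalities during the study will be tabulated". SAP 8.6 turns this into a count and percentage by dose level of potentially clinically significant (PCS) values. The numerator is "patients who had at least one PCS assessment post baseline", among those in the denominator. On the baseline side, "the denominator of the percentage will include patients with non-PCS or missing assessments at baseline", and any one later assessment is enough to qualify. SAP 8.6 then adds: "Assessment collected at an unscheduled visit or the Follow-up Visit will also be included in the summary". SAP 8.4 (values outside the laboratory range) and SAP 8.5 (PCS vital signs and weight) carry the same rule.

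Under Protocol 5.13.2, ECGs "will be obtained at Screening, Week 4 visit, and at the Follow-Up Visit". The Week 4 ECG is listed in Protocol 5.4 under "Prior to study drug dosing at the Week 4 Visit, the following procedures will be performed", so it is taken before that day's clinic dose in a patient on twice-daily drug. Table 2 of the Protocol places Follow-Up 4 weeks after the last dose, ±4 days. Protocol 5.8 adds an ECG at the Early Termination Visit.

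Neither document plans an on-treatment count of abnormalities, or a count by visit, for ECG, laboratory or vital signs. Protocol 8.4.5.7 does plan counts by visit for physical and neurological examinations.

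**The concern.** Clinically important changes in ECG, laboratory tests and vital signs are a stated safety endpoint (Protocol 8.3.2), and the study is meant to guide dose selection for Phase 3 (Protocol 3.3). The natural safety question is how often each arm shows an abnormality while exposed. The planned table answers a different one: how often each arm shows an abnormality at any time after baseline, including a month after exposure has ended.

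Abnormalities that first appear at a drug-free visit are background. They add cases to every arm and so bring the arm percentages closer together in ratio. ECG is the most exposed, because half of a completer's scheduled post-baseline ECGs are off drug. Weight is exposed for another reason: the 5% loss flag in SAP Table 6 compares with baseline, and Protocol 7.4.3 lists weight loss as an expected sign of ALS progression, so a further month can add cases whatever the treatment.

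**Working it through.** **The plan's own figures.** The documents give no abnormality rate for any of these measures. The only design figure is 90% power for the primary SVC contrast. It reproduces: contrast value −1×2.75 + 3×5.5 + 3×5.5 = 30.25; standard error 14×√(44/100) = 9.287; power Φ(30.25/9.287 − 1.96) = 0.903. Its only use here is arm size: 445/4, about 111 patients.

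**Is Follow-Up drug-free?** Protocol 1.3 gives half-lives of about 12 h (parent) and 25.4 to 39.3 h (metabolite, described as inactive). 28 days = 672 h, so 672/12 = 56 parent half-lives and 672/39.3 = 17 to 672/25.4 = 26 metabolite half-lives. At the earliest window day (24 days = 576 h) the figures are 48 for the parent and 576/39.3 = 14.7 for the slowest metabolite value. Essentially nothing remains.

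**Effect on the count.** Let p be the proportion flagged on drug, and f the chance that a patient not flagged on drug is first flagged at Follow-Up, taken as equal in all arms. Then

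- ever-flagged = p + (1 − p)f = 1 − (1 − p)(1 − f);
- difference between arms = (p1 − p0)(1 − f), where 1 is active and 0 is placebo.

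All rates below are assumptions. If the two readings are independent, f is simply the Follow-Up abnormality rate.

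| p0, p1, f | Ever-flagged, placebo v active | Difference, on drug → planned count | Ratio, on drug → planned count |
|---|---|---|---|
| 3%, 10%, 3% | 5.9% v 12.7% | 7.0 → 6.8 points | 3.3 → 2.15 |
| 2%, 6%, 2% | 3.96% v 7.88% | 4.0 → 3.92 | 3.0 → 1.99 |
| 5%, 10%, 5% | 9.75% v 14.5% | 5.0 → 4.75 | 2.0 → 1.49 |
| 5%, 15%, 10% | 14.5% v 23.5% | 10.0 → 9.0 | 3.0 → 1.62 |
| 0.5%, 2%, 0.5% | 1.0% v 2.49% | 1.5 → 1.49 | 4.0 → 2.5 |
| any p0 and p1, f = 0 | unchanged | unchanged | unchanged |

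The last numeric row stands for a rare criterion such as QTc above 500 msec. Follow-Up then adds about 0.005 × 111 = 0.6 patient per arm, so the fall in ratio rests on a handful of cases.

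**Within-patient correlation.** Take the first row and give background abnormality a correlation r between the two readings. Then P(both abnormal) = 0.03² + r×0.03×0.97 and f = (0.03 − P(both))/0.97. For r = 0.3, 0.5 and 0.7, f is 2.1%, 1.5% and 0.9%, and the ratio is 2.36, 2.55 and 2.79. If every Follow-Up abnormality is in a patient already abnormal at Week 4, f = 0 and nothing changes.

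**Laboratory.** There are three on-drug visits (Weeks 2, 4 and 12) and one off-drug visit. With independent readings at 3% v 10% per visit, the on-drug counts are 1 − 0.97³ = 8.7% v 1 − 0.90³ = 27.1%, ratio 3.10. With Follow-Up they are 1 − 0.97⁴ = 11.5% v 1 − 0.90³×0.97 = 29.3%, ratio 2.55.

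**Denominator.** A patient whose only post-baseline ECG is at Follow-Up still counts. If 10% of patients were like that (an assumption), the share of the on-drug difference retained would be 0.90×0.98 = 88% in the second row and 0.90×0.95 = 86% in the third.

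**The case against.** The strongest reply is that an ever-abnormal count loses nobody. A reader might infer that an on-drug excess is hidden; the arithmetic does not support that, since 98% of the difference is kept at f = 2%, 95% at 5% and 90% at 10%. That stands.

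A reader might also infer a loss of power. In the first row, a Fisher test at 111 per arm would flag the excess 48% of the time on drug and 34% of the time on the planned count. But Protocol 8.4.5 makes the safety summaries descriptive and no test of PCS counts is planned, so those figures describe no planned decision.

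Nor do the by-visit tables give means only. SAP 8.6 promises descriptive statistics at each time point by dose level, and SAP 5.1 defines these to include median, minimum and maximum. The largest Week 4 QTc in each arm will therefore be visible, and PCS values are flagged in listings with visit and date. This mitigates the problem in part, but it yields no proportion of patients abnormal on drug.

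Counting all post-baseline findings is also a coherent choice. It captures delayed effects, and adverse events too are collected through Follow-Up (Protocol 7.3.1). This is a good reason to keep the planned count. Finally, the single on-drug ECG is single only among scheduled readings in completers; unscheduled and early-termination ECGs also enter.

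**Conclusion.** The point holds as a minor one. The planned counts combine exposed and drug-free assessments, and the plan has no on-drug abnormality rate by arm. The absolute difference is almost unchanged; the ratio falls, by an amount that depends on how often patients are first flagged at Follow-Up, which the documents do not give. The assumption of independent readings leans toward more dilution.

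The effect is negligible in patient numbers for rare criteria. It matters mainly for flags that may be common in this population: ventricular rate above 100 bpm, respiration rate above 18 and weight loss of at least 5%. The documents do not support the stronger conclusion that the planned count is wrong or should be demoted to supportive.

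**What to change.** In SAP 8.4 to 8.6, add a count and percentage by dose level of patients with an abnormal or PCS value on treatment, with its own denominator of patients assessed in that period. Define the period by dose dates: from first dose to last dose plus a short interval stated before unblinding, including unscheduled and early-termination records that fall inside it. Five half-lives would be 5×12 = 60 h (2.5 days) for the parent and 5×25.4 to 5×39.3 h (5.3 to 8.2 days) for the metabolite; the sponsor should choose and justify the interval.

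Do not split by the SAP Appendix B analysis visit. An unscheduled or early-termination ECG from Day 71 falls in the Follow-up window even if the patient is still on drug, and one up to Day 70 falls in the Week 4 window even if dosing has stopped. Vital signs can also be off drug before Follow-Up, because Protocol 5.15 encourages patients who stop drug to attend their remaining visits.

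Show later, off-drug assessments in a separate column, so that delayed effects stay visible, and keep the planned all-post-baseline count. The change uses data already collected and does not affect conduct. The cost is SAP wording and slightly larger tables.

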8.4.5.7. Physical and Neurological Examinations

The number and percentage of subjects deemed by the investigators to have clinically significant abnormalities will be tabulated by type of exam at each scheduled visit where physical or neurological examinations are taken. All measurements identified as clinically relevant abnormalities will be listed.

8.4.5.8. Ashworth Score

Ashworth score will be determined bilaterally at the elbows and knees with the results summarized at each body location.

8.4.5.9. Falls Assessments

The number and percentage of subjects with falls will be tabulated at each scheduled visit where falls assessments are taken. Activities engaged at the time of the fall, physical symptoms experienced immediately preceding the fall, and if the fall resulted in injury will also be summarized.

8.4.5.10. Beck Depression Inventory-Fast Screen

The total score of the BDI-Fast Screen is determined by summing the scores from the 7 questions, and can range from 0 to 21, with higher scores indicating greater depression severity. The value and change from baseline in the total score of the BDI-Fast Screen will be summarized at each scheduled visit where scores are taken.

8.4.6. Exposure-Response Analysis

The relationship of drug exposure with efficacy and safety endpoints of interest will be explored. Graphical and tabular presentations will be provided as appropriate.

8.4.7. Pharmacokinetic Analysis

PK analyses will be conducted using the PKS. All of the PK samples collected, including those obtained at Hour 3 on Day 1 as well as Hour 3 and Hour 6 at Week 2 and Week 12 from patients enrolled prior to Amendment 03, will be used for PK analyses. PK parameters such as t_{max} , C_{max} ,

C_{trough} , AUC_{0-24} , AUC_{∞} , CL/F , V/F , $t_{1/2}$ and R_{AC} will be summarized by dose group using descriptive statistics as appropriate. Nominal sample times will be presented in all statistical and graphical summaries.

The observed plasma concentrations of CK-2127107 and its metabolites (if applicable) and riluzole at planned sampling time points will be summarized and listed. The potential for drug-drug interaction between CK-2127107 given alone and in the presence of riluzole will also be assessed.

The PK parameters with and without co-administration of riluzole will also be summarized. Box-whiskers-plots of AUC and C_{max} at Visit Week 12 with and without co-administration of riluzole will be presented.

8.5. Interim Analysis

After the last patient completes dosing, an interim analysis may be conducted by the Sponsor.

8.6. Statistical Software

Statistical analyses will be performed using SAS® version 9.4 or greater.

8.7. Changes in Statistical Methods

All changes in statistical methods that are described in the statistical analysis plan will be documented in the clinical study report.

9. ADMINISTRATIVE ASPECTS

9.1. Change in Protocol

There will be no alterations in the protocol without agreement between the Sponsor and the Investigator. There will be no alterations in the protocol without the express written approval of the Sponsor, Investigator, and the Institutional Review Board (IRB)/Research Ethics Board (REB)/Ethics Committee (EC) and regulatory authorities, as applicable.

9.2. Initiation Visit

Prior to the start of the clinical study at each site, the representative(s) of the Sponsor will meet with the Investigator(s) and appropriate clinical staff to familiarize the Investigator and clinical staff with the materials necessary for conducting the clinical study.

9.3. Disclosure

All information provided regarding the study, as well as all information collected/documented during the course of the study, will be regarded as confidential. The Investigator agrees not to disclose such information in any way without prior written permission from the Sponsor.

Any publication of the results, either in part or in total (e.g., articles in journals or newspapers, oral presentations, abstracts, etc.) by the Investigator(s) or their representative(s), shall require prior notification and review, within a reasonable time frame, by the Sponsor, and cannot be made in violation of the Sponsor's confidentiality restrictions or to the detriment of the Sponsor's intellectual property rights.

